## **METHODS**

We wrote a investigation protocol which has already been approved by the Research Ethics Committee of Hospital Universitario La Paz, Madrid.

This is a prospective experimental study; blind randomized, with parallel groups and final blind analysis with, at least, 64 patients with chronic pain.

All patients will be assessed at the pre-intervention moment, at the post-intervention moment (8 weeks), and in a 6 months follow-up.

This is a pre-post experimental design with which we intend to compare the effectiveness of 2 psychotherapeutic treatments for chronic pain. The two arms of treatment of this Randomized Clinical Trial are:

a) Mindful Self-Compassion Program (MSC)

b) Cognitive-Behavioural Program for chronic pain (CBT).

Both treatments are conducted by experimented clinicians with wide experience in chronic pain. We will conduct 8 therapeutic groups in total (4 for each arm treatment), with approximately 15 people per group.

We have estimated that we need a N=64 in order to detect significant differences in the principal outcome (self-care and self-compassion) with a size effect=0.5, SD=0.6, alpha=0.05 and power=90%.

During the investigation we will create a Data Base in accordance with current regulations. Data will be use following the principles contained in the Organic Law 15/1999, 13th December, of Personal Data Protection. All data will be electronically introduced in this database and data analysis will be conducted using SPSS 18.0.

It will be conducted an exploratory study of all variables previous to statistical analysis in order to identify anomalous data.

It has been done a first-step approximation to the behaviour and variability of the main outcome of the study with a 30 patients simple randomized to both arms in order to estimate the necessary N of the study.

Descriptive analysis of qualitative variables will be expressed in terms of frequencies and percentage, and analysis of quantitative variables will be expressed in terms of mean, standard deviation, median and interquartile range. The analysis will be conducted by intention to treat. Comparison of qualitative variables between groups of interventions or between segmentation factors will be conducted with Fisher test. We will apply t-Student, Mann-Whitney, ANOVA or Kruskal-Wallis test in quantitative variables, depending on the normality of the variable (tested with Kolmogorov-Smirnov-Lilliefords test) and the number of compared categories..

Analysis of the changes along the treatment on principal and secondary outcomes of effectiveness will be conducted through a General Lineal Model (ANOVA with repeated measures), which allows checking if there are statistical significant differences in these changes based on arm of intervention.

Regression models will be conducted in order to identify prognostic factors.

Variables "Treatment satisfaction" and "adherence to treatment" will be compared using t-Student test for independent samples for patients who complete the treatment.

Aetiology of chronic pain will be taken into account when it is known.

Given the shortage of studies until the date referred to the effects of interventions based on self-compassion in chronic pain patients, the results of this study may give empirical date about the effectiveness and the need of mindful-self-compassion-based interventions, integrated in a multidisciplinary, approach to improve quality of life and self care in chronic pain patients.

Now, we go on to describe the two arms of treatment tested in this study:

- Mindfulness Self-Compassion (MSC) is a standardized program to increase self-compassion. It has been developed by Neff and Germer. The structure of the program is similar to de Mindfulness-Based Stress Reduction program (MBSR), with duration of sessions between 2 and 2 hours and a half. The frequency of the sessions is one per week for 8 weeks, with practical and experiential exercises in sessions and between sessions. The MSC program focuses primary on helping patients to develop self-compassion, and it includes Mindfulness just as a secondary component. The MSC program will be conducted by a clinician trained in this specific program.

- CBT: It has been adapted a Cognitive-Behavioural Intervention for Chronic Pain by Moix and Kovacs. Our program will have 8 sessions, with duration of sessions between 2 and 2 hours and a half. The frequency of the sessions is one per week for 8 weeks, with homework between sessions. During these 8 sessions we will train the following techniques: psycho-education about pain, relaxation training, cognitive restructuring training, solving problem training, psycho-education about emotions, interpersonal skills and time organization.

There we present the variables of the study:

Primary Outcome Measure:

- Self-Compassion: Self-Compassion Scale (SCS, long version). Self-compassion and Self-care. Self-kindness, Common Humanity and Mindfulness.

[Time Frame: At the beginning of the intervention, at the end of the intervention and at a 6 months follow-up]

Secondary Outcome Measures:

- Acceptance: Chronic Pain Acceptance Questionnaire (CPAQ). Activity engagement, Pain

willingness. [Time Frame: At the beginning of the intervention, at the end of the intervention and at a 6 months follow-up]

- Pain Interference: Pain interference in daily life. Brief Pain Inventory (BPI): pain intensity and impact of pain in daily life. [Time Frame: At the beginning of the intervention, at the end of the intervention and at a 6 months follow-up]

- Pain Intensity: Analogical Visual Scale.[Time Frame: At the beginning of the intervention, at the end of the intervention and at a 6 months follow-up]

- Catastrophising: Pain Catastrophising Scale (PCS). Rumination, magnification of consequences and hopelessness [Time Frame: At the beginning of the intervention, at the end of the intervention and at a 6 months follow-up]

- Quality of life: SF-36. Physical function, physical role, body pain, general state of health, vitality, social function, emotional role and mental health.[Time Frame: At the beginning of the intervention, at the end of the intervention and at a 6 months follow-up]

- Anxiety and Depression Levels of anxiety and depression. Symptomatology. Hospital Anxiety and Depression Scale (HADS). [Time Frame: At the beginning of the intervention, at the end of the intervention and at a 6 months follow-up]

- Satisfaction with the treatment Satisfaction with the treatment (CRES-4) [Time Frame: At the end of the intervention]

- Adherence to the treatment Adherence to the treatment (Number of sessions that one patient attends) [Time Frame: At the end of the intervention]

Other Pre-specified Outcome Measures:

- Socio-demographic Data: Age, gender, marital status, family life, job status, time with pain, type of pain, psychiatric history, course pain expectation, number of visits to emergency units in the last 3 months, number of visited doctors in the last 3 months. [Time Frame: At the beginning of the intervention]

Inclusion and exclusion criteria are as follow:

- Inclusion Criteria:
  - Older than 18 years old.
  - Being in treatment in the Chronic Pain Unit at Hospital Universitario La Paz because of having a chronic pain of more than 3 months of duration, no matter the aetiology.
  - Capable of understanding and giving his or her written informed consent.
  - Significant levels of distress and disability related to the pain at the beginning of treatment, assessed by clinical interview and HADS (> or = 8).
  - Significant levels of pain interference in daily life assessed by sub-scale of interference of the Brief Pain Inventory (> or = 5).
  - Significant levels of "catastrophising" at the beginning of the treatment assessed by Pain Catastrophising Scale (PCS) (> or = 30).
  - Patients that meet criteria for Mixed Adaptive Disorder, mild to moderate Depressive Disorder or Dysthymia, assessed by clinical interview conducted by a psychiatry of the Chronic Pain Unit or Mental Health Centre.
- Exclusion Criteria:
  - Intellectual disability or cognitive impairment or dementia.
  - Insufficient knowledge of the language to understand and participate on the intervention program.

- Serious mental illness in acute state at the moment of the beginning of the intervention.
- Substance abuse in the last 6 months.
- Autolytic ideas at the moment of the assessment.
- Previous training in mindfulness or CBT techniques.

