## **OBJECTIVES AND HYPOTHESIS**

The objective of this study is to analyse the effectiveness of the MSC program versus the CBT program in order to improve self-care, compassionate relation to oneself, quality of life in a chronic pain patient’s sample. Both treatments are conducted in groups, are psychotherapeutic oriented, both have an 8 weeks duration, weekly frequency, 2 and a half hours per session.

The principal hypothesis of this investigation is:

- MSC program will be, at least, as effective as the CBT program in order to improve self-care capacity and self-compassion in chronic pain patients (decreasing self-criticism, isolation feelings, and thoughts over-identification) at the post-treatment time and in a 6-months follow-up.

Secondary hypothesis:

- MSC program will be, at least, as effective as CBT program in order to improve quality of life, and acceptance capacity; and as effective as CBT to reduce catastrophizing, daily life interference, anxiety and depression in a chronic pain patients simple, at the post-treatment time and a 6 months follow-up.

- We also hypothesize that MSC program will be, at least, as effective as CBT program in order to maintain the achieved benefits in a 6 months follow-up.

- Treatment satisfaction will be higher in MSC program, being treatment adherence higher in this program than in CBT program.

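### Both treatments are given in therapy groups, but the sample size and the between-arm tests treat patients as independent, so type I error exceeds 5% if outcomes correlate within groups

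*Combined protocol and SAP*

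**What the plan says.** The OBJECTIVES AND HYPOTHESIS section says of MSC and CBT: "Both treatments are conducted in groups, are psychotherapeutic oriented". METHODS gives the number and size of the groups: "We will conduct 8 therapeutic groups in total (4 for each arm treatment), with approximately 15 people per group".

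The sample size paragraph in METHODS justifies 64 patients by "size effect=0.5, SD=0.6, alpha=0.05 and power=90" (per cent). The same section treats 64 as a minimum: "final blind analysis with, at least, 64 patients with chronic pain". It mentions no ICC, design effect or other allowance for therapy group.

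Three kinds of between-arm analysis are planned in METHODS:
- a general list: "We will apply t-Student, Mann-Whitney, ANOVA or Kruskal-Wallis test in quantitative variables", chosen by normality and number of categories;
- for change in the primary and secondary outcomes, an analysis that "will be conducted through a General Lineal Model (ANOVA with repeated measures"), with arm as the only grouping factor named;
- for satisfaction and adherence, variables that "will be compared using t-Student test for independent samples for patients who complete the treatment".

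None has a therapy-group term or a cluster-robust standard error.

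**The concern.** Individual randomisation makes patients independent at baseline, but not after eight weekly sessions with the same people. Group dynamics, group attendance and the way a clinician runs a particular group can all make members' post-treatment scores more alike. Because both arms are group-delivered, this affects both sides of the comparison.

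Patient-level tests estimate the variance of an arm mean as if each patient supplied separate information. With positive within-group correlation that variance is too small. P-values for MSC versus CBT are then too small and confidence intervals too narrow. The harm is not confined to false claims of a difference. The principal hypothesis is that MSC does no worse than CBT, and a conclusion of that kind read from a confidence interval would also be reached too easily.

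A second question is power. The minimum of 64 implies 8 patients per group, while 8 groups of about 15 make about 120 places. The two are compatible, but the plan does not say which enrolment its power statement describes.

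**Working it through.** **Inputs from METHODS.** Difference 0.5, SD 0.6, alpha 0.05, power 90%, minimum N = 64, 8 groups (4 per arm), about 15 per group.

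**Assumptions.** Equal allocation; two-sided test (sidedness is not stated, but two-sided reproduces 64 and one-sided gives 50); ICC of 0.01, 0.05 or 0.10; group size m = 8 (64/8) or m = 15 (stated).

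**Step 1: reproduce the plan's figure.** The standardised difference is 0.5/0.6 = 0.833. Noncentral-t power for independent patients is 89.8% at 31 per arm and 90.7% at 32 per arm. So 2 × 32 = 64 is exactly the independent-patient size and contains no allowance for clustering.

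**Step 2: variance inflation.** Design effect DE = 1 + (m − 1) × ICC; effective N = N/DE.

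| | ICC 0.01 | ICC 0.05 | ICC 0.10 |
|---|---|---|---|
| m = 8: DE | 1.07 | 1.35 | 1.70 |
| Effective N of 64 | 59.8 | 47.4 | 37.6 |
| m = 15: DE | 1.14 | 1.70 | 2.40 |
| Effective N of 120 | 105.3 | 70.6 | 50.0 |

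The unadjusted standard error is too small by a factor √DE: 1.03 to 1.30 for m = 8, and 1.07 to 1.55 for m = 15.

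**Step 3: type I error of the unadjusted tests.** A quick approximation is 2 × [1 − Φ(1.96/√DE)]. At m = 8 and ICC 0.05, 1.96/√1.35 = 1.687, giving 9.2%. At m = 15 and ICC 0.05, 1.96/√1.70 = 1.503, giving 13.3%. Simulation with 4 groups per arm agrees:

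| Test | ICC 0.01 | ICC 0.05 | ICC 0.10 |
|---|---|---|---|
| t-test, m = 8 | 5.8% | 9.3% | 13.5% |
| t-test, m = 15 | 6.7% | 13.4% | 21.0% |
| Arm-by-time ANOVA, m = 8 | 5.9% | 9.2% | 13.3% |
| Arm-by-time ANOVA, m = 15 | 6.4% | 13.5% | 21.0% |

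The t-test rows use 200,000 runs and the ANOVA rows 40,000. The ANOVA has three occasions, an assumed within-patient correlation of 0.5, and a group effect at both post-baseline visits only. With ICC 0 the ANOVA rejected in 4.8–5.0% of runs.

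**Step 4: power when the error rate is held at 5%.** Two calculations bracket it. The first puts effective N into the t-test of Step 1. The second is a t-test on the 8 group means with 8 − 2 = 6 degrees of freedom (df). There the variance of a group mean is SD² × [ICC + (1 − ICC)/m], and the standard error of the difference is √(2 × variance/4). At m = 8 and ICC 0.05:
- variance = 0.36 × (0.05 + 0.95/8) = 0.06075;
- standard error = √(2 × 0.06075/4) = 0.174;
- noncentrality = 0.5/0.174 = 2.87;
- power = 67%.

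| Power | ICC 0.01 | ICC 0.05 | ICC 0.10 |
|---|---|---|---|
| N = 64, effective N | 89% | 80% | 70% |
| N = 64, 6 df | 77% | 67% | 57% |
| N = 120, effective N | 99% | 93% | 82% |
| N = 120, 6 df | 94% | 83% | 69% |

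At 120 patients, power stays at 90% or more up to an ICC of about 0.066 (effective N) or 0.026 (6 df). The 6-df test of baseline-adjusted group means kept its type I error at 4.9–5.1% in every scenario.

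**The case against.** The best case for the plan has five parts.

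- **The ICC is unknown and may be small.** This is true. At 0.01 the excess error is under 2 percentage points, so the size of the harm is a range. But the plan neither estimates the ICC nor argues that it is negligible.
- **The planned test does not lose as much power as Step 4 shows.** At N = 64 the unadjusted t-test rejects in about 90%, 88% and 85% of simulations when the difference of 0.5 is real. Those rates are bought with a type I error above 5%, so the stated pair of 5% alpha and 90% power is still missed. It is fair that the 6-df power of 79% at N = 64 with ICC 0 is a cost of that test and not evidence of a defect.
- **The power figures may be pessimistic for the recommended model.** They describe one unadjusted comparison. METHODS does not say whether SD 0.6 is for a score or a change; if it is for a score, baseline adjustment would recover some power. This stands as a caveat.
- **The stated group size is 15, not 8.** Eight per group follows only from spreading the minimum of 64 over 8 groups. At about 120 the power problem shrinks, but the type I error problem grows (13.4% against 9.3% at ICC 0.05).
- **The general list of tests is not tied to post-treatment outcomes.** It may cover baseline or subgroup comparisons. That is a fair reading, but the repeated-measures ANOVA and the satisfaction and adherence t-test do concern outcomes arising during or after treatment.

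**Conclusion.** The concern holds. The design creates clusters in both arms, the sample size ignores them, and no planned between-arm analysis accounts for them. Type I error is the main issue: over an assumed ICC of 0.01 to 0.10 it runs from about 6% to 13% at 64 patients, and from about 6% to 21% at about 120. Power is secondary. At the minimum of 64, the stated 90% is not reached by a valid analysis at any ICC in that range. At about 120 it may be.

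The omission is certain. Its size rests on the assumed ICCs, equal allocation and equal group sizes, and, for the ANOVA, a group effect that appears only after baseline. If the ICC were zero, the planned tests would keep their nominal level.

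**What to change.** 1. **Record therapy group** for every patient. The documents do not say that this is captured.
2. **Primary and secondary outcomes.** Replace the repeated-measures ANOVA with a linear mixed model of the post-treatment and 6-month values, adjusted for baseline, with therapy group (nested in arm) as a random effect, patient as the repeated unit, and Satterthwaite degrees of freedom. If baseline is kept as an outcome, the random effect must be group by post-baseline time, because a group intercept constant over time cancels from the arm-by-time contrast and repairs nothing.
3. **Satisfaction and adherence.** Use the same group random effect.
4. **Sensitivity analysis.** Compare baseline-adjusted group means on 6 df. With 8 groups the variance component may be estimated as zero. In a simplified single-outcome version with 8 per group this happened in 22–57% of runs, with type I error of 3.1–4.8%: conservative, not invalid.
5. **Power.** Say whether the statement describes 64 or about 120 patients, give power over ICC 0.01–0.10, and report the estimated ICC with the results.

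The cost is one data field to confirm or add, a changed model and a rewritten power paragraph, with no additional enrolment. Intervals will be wider because only 8 groups inform the comparison, and stated power will fall below 90% if enrolment stays near 64. A group random effect cannot separate a clinician's effect from the arm's if one clinician leads all groups of an arm. Whether SPSS 18.0, the named software, offers the required degrees of freedom should be checked; the group-means comparison needs only an ordinary t-test once the means have been adjusted for baseline.

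### Intention to treat is promised with no rule for missing assessments; one default three-visit repeated-measures ANOVA would make the result complete-case

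*Combined protocol and SAP*

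**What the plan says.** In Methods, the analysis population is a single sentence: "The analysis will be conducted by intention to treat". The analysis of change in the principal and secondary effectiveness outcomes "will be conducted through a General Lineal Model (ANOVA with repeated measures". That sentence lists no visits. The visits come from elsewhere in Methods: "All patients will be assessed at the pre-intervention moment, at the post-intervention moment (8 weeks), and in a 6 months follow-up". The Self-Compassion Scale (SCS), the primary outcome, has the time frame "At the beginning of the intervention, at the end of the intervention and at a 6 months follow-up". Under Objectives and Hypothesis, the principal hypothesis is to be judged "at the post-treatment time and in a 6-months follow-up", so both follow-up times matter. On software, "data analysis will be conducted using SPSS 18.0".

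The text available to this review has no definition of the intention-to-treat set, no imputation rule, no missing-data assumption, no sensitivity analysis and no dropout allowance. The only data check before analysis is a screen for anomalous values.

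**The concern.** Intention to treat says in which arm a randomised patient is analysed. It does not say what happens when that patient's outcome is missing, so the analysis method decides. A classical repeated-measures ANOVA needs a full set of values for each patient, and its usual default is to drop anyone with a gap. That is a property of the method, not a statement in the plan.

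Over three visits, this default discards 8-week scores that were actually collected, because the same patient did not return at 6 months. The 8-week half of the principal hypothesis would then rest on patients selected by later attendance. Precision is lost in any case. Bias follows if that selection is related to outcome in different ways in the two arms. As written, a reader cannot tell which randomised patients the primary result will contain, and the choice could be made after the data are seen.

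**Working it through.** **1. The plan's own sample size.** Inputs from Methods: difference 0.5, SD 0.6, alpha 0.05, power 90%. Two-sided testing and 1:1 allocation are assumed. The two-sample t-test needs 31.25 per arm, hence 32 per arm and 2 × 32 = 64, as stated. The 64 is therefore a number of analysable patients, with no allowance for loss. Methods also plans 8 groups of about 15, which is about 120 places.

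**2. Does power drive the concern?** With 60 per arm, 90% power is kept until loss reaches 1 − 31.25/60 = 0.48, before any allowance for therapy groups. With exactly 64 randomised, the limit is 1 − 62.5/64 = 0.02. So power is not a reason for the change if about 120 are enrolled.

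**3. 8-week data discarded by one default three-visit model.** Assumptions: 10% missing at 8 weeks and, independently, a share p missing at 6 months. Observed at 8 weeks: 0.9N, which is 108 (N = 120) or 57.6 (N = 64). Retained: 0.9N(1 − p). Standard error ratio: 1/√(1 − p).

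| p at 6 months | Retained, N = 120 | Retained, N = 64 | SE ratio at 8 weeks |
|---|---|---|---|
| 10% | 97.2 | 51.8 | 1.054 |
| 20% | 86.4 | 46.1 | 1.118 |
| 30% | 75.6 | 40.3 | 1.195 |

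Under separate two-visit models the 8-week comparison keeps all 108 (or 57.6), and this loss does not occur.

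**4. Bias, by simulation.** Assumptions: 6000 replicates per cell, N = 120, SD 0.6, no true difference, 8-week data complete. Log-odds of missing 6 months = log(0.2/0.8) + slope × (8-week score in SD units), with the slope set by arm. All correlations are 0.5 unless stated. Entries are the mean arm difference in change from baseline (standard error); the truth is 0.

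| Analysis | Slopes by arm | 8 weeks | 6 months |
|---|---|---|---|
| Complete cases | 0 and 1 | −0.062 (0.122) | 0.001 (0.125) |
| Complete cases | 0 and 0.5 | −0.029 (0.124) | not tabulated |
| Complete cases | 1 and 1 | 0.001 (0.124) | not tabulated |
| Complete cases | 0 and 0 | 0.001 (0.121) | not tabulated |
| All observed 8-week values | 0 and 1 | −0.001 (0.109) | – |
| Complete cases, correlations 0.5/0.4/0.7* | 0 and 1 | −0.059 (0.124) | −0.023 (0.137) |

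*Baseline–8 weeks, baseline–6 months, 8 weeks–6 months.

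Repeat runs of the one-arm scenario (slopes 0 and 1) gave −0.061 to −0.063 at 8 weeks and, with the unequal correlations, −0.022 to −0.027 at 6 months. Loss in that scenario is 20% in one arm and 24% in the other.

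**5. Plausibility checks.**
- With correlation 0.5 the SD of change is 0.6 × √(2 × 0.5) = 0.6, so with 60 per arm the standard error is 0.6 × √(2/60) = 0.110. The simulated value is 0.109.
- Selection acts only through the 8-week score. The 6-month shift should therefore equal the 8-week shift times (r₈,₆ₘ − r₀,₈)/(1 − r₀,₈). With equal correlations this factor is 0. With the unequal set it is (0.7 − 0.5)/(1 − 0.5) = 0.4, and 0.4 × (−0.059) = −0.024. Both agree with the table.

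**6. Size in context.** At 8 weeks, 0.06/0.12 is half a standard error, and 0.06/0.5 is 12% of the design difference. A two-sided 5% test shifted by half a standard error rejects with probability Φ(−1.46) + Φ(−2.46) ≈ 0.072 + 0.007 ≈ 8%.

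**7. The alternative.** A likelihood mixed model with baseline by visit, in the one-arm scenario, gave −0.002 (0.095) at 8 weeks and 0.001 (0.108) at 6 months. With the unequal correlations it gave 0.003 (0.095) and 0.002 (0.110). Loss here is missing at random by construction, so the near-zero shift is expected. Part of the smaller standard error comes from the baseline covariate, not from recovered data.

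**The case against.** The strongest reply is that the plan never says incomplete patients will be dropped. Listwise deletion across visits needs three things that the text does not fix: one model over all three visits, default handling, and no imputation. Methods speaks of change over the course of treatment and calls the design pre-post, and both fit a baseline-to-8-week model. It also lists simple two-group tests for quantitative variables; if these cover outcomes at each visit, they would use every observed 8-week value. This stands, and it is why the complete-case result can only be stated conditionally. It does not remove the gap. Each two-visit model would still omit patients who missed that visit, and the plan does not say which model is meant.

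Second, every loss rate, correlation and loss mechanism above is assumed, and the bias is modest even in an unfavourable case. This also stands.

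Third, the gap could be closed without abandoning the planned model, by imputing first. That is right, and imputation is offered below as an equal option. A mixed model also leaves out patients with no follow-up value, so it does not by itself complete the intention-to-treat promise.

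A reader might go further and infer that the plan commits to a complete-case primary analysis, that the primary result will be biased, or that the trial will be underpowered. The documents support none of these. No exclusion is stated, nothing shows that loss will differ by arm, and about 120 places leave ample room for loss. The expectation of better adherence with MSC concerns sessions attended, not assessments returned.

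**Conclusion.** The concern holds as an omission with a conditional consequence. Intention to treat is stated, but which patients enter the primary result and how missing assessments are handled are not. If one repeated-measures ANOVA is run by default over three visits without imputation, the 8-week result is complete-case. It then discards the same share of observed 8-week values as is missing at 6 months, and the standard error rises by about 5, 12 or 20% at an assumed 10, 20 or 30%.

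Bias arises only if loss depends on outcome differently by arm. In the unfavourable scenario at N = 120 it is about −0.06 at 8 weeks and between 0 and about −0.03 at 6 months. It is zero for symmetric loss. These sizes rest on assumed loss, correlations and mechanism, and the documents cannot narrow them. The point should be corrected before analysis, but it does not undermine the design. The completer-only comparisons of satisfaction and adherence, and the relation between 64 patients and about 120 places, are separate matters and not part of this finding.

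**What to change.** In the Methods paragraph on effectiveness analysis, adopt one of two options for SCS and state it in advance:

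- **Mixed model.** Replace the repeated-measures ANOVA with a likelihood-based mixed model for repeated measures in SPSS MIXED. Outcome: SCS at 8 weeks and 6 months. Fixed effects: arm, visit, arm × visit, and baseline SCS with a slope that may differ by visit. Covariance: unstructured.
- **Multiple imputation** before the planned General Linear Model, with the imputation model described.

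Under either option, analyse patients in their assigned arm and report the arm difference with a 95% confidence interval at each visit. State that the main analysis assumes data are missing at random. Add one missing-not-at-random sensitivity analysis that includes randomised patients with no follow-up value.

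The cost is SAP wording and slightly more analysis work in the software already named. Visits, recruitment and treatment do not change. The drawback is that the main analysis relies on missing at random, which the data cannot confirm; the sensitivity analysis is there to test that reliance. Any allowance for therapy group is a separate matter and can be added to whichever model is used.

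### The effectiveness analysis compares changes over the visits without adjusting for the baseline score; adjusting is a free gain in precision, and the plan should say which SD the 0.6 behind N=64 is

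*Combined protocol and SAP*

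**What the plan says.** All references are to the METHODS section of the combined protocol and SAP.

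- **Analysis.** The analysis of principal and secondary effectiveness outcomes "will be conducted through a General Lineal Model (ANOVA with repeated measures), which allows checking if there are statistical significant differences in these changes" by arm. No baseline covariate is named. Regression models are mentioned only for finding prognostic factors.
- **Visits.** The time frame of the primary outcome, the SCS, is "At the beginning of the intervention, at the end of the intervention and at a 6 months follow-up". The secondary scales (CPAQ, BPI, the visual analogue scale for pain, PCS, SF-36, HADS) have the same three visits. Only satisfaction and adherence are recorded once, at the end.
- **Sample size.** "We have estimated that we need a N=64 in order to detect significant differences in the principal outcome", on the inputs "size effect=0.5, SD=0.6, alpha=0.05 and power=90" (per cent). The variability was studied in a "first-step approximation to the behaviour and variability of the main outcome of the study with a 30 patients simple randomized to both arms". The plan does not say whether 0.6 is the SD of a score at one visit or of a change, and gives no correlation between visits.
- **Size in practice.** The study is described as having "final blind analysis with, at least, 64 patients with chronic pain". The same section adds: "We will conduct 8 therapeutic groups in total (4 for each arm treatment), with approximately 15 people per group".

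**The concern.** A comparison of changes over these three visits appears to use baseline as one level of the time factor, in effect subtracting it from the later scores. That is not the most precise use of a baseline score. Subtraction removes the whole baseline value, although only a fraction rho of it carries over to follow-up (taking equal SDs), and so it adds noise when rho is modest. Entering baseline as a covariate removes only the part that predicts the outcome. It also corrects for a chance difference between arms at baseline, whereas subtraction over-corrects for one.

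The sample-size statement names no correlation and reproduces as a simple two-group comparison. The reader therefore cannot tell whether the 90% refers to the change analysis that the plan describes. At stake are the width of the confidence intervals for SCS and six secondary measures and, if only the minimum of 64 is analysed, possibly some power.

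**Working it through.** **Inputs from the plan:** N=64, difference 0.5, SD 0.6, alpha 0.05, power 90%.

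**Assumptions:** 1:1 allocation (four groups per arm), so 32 per arm; two-sided alpha; 0.5 as a raw difference, because an SD stands beside it; equal SDs and equal correlations rho at all visits; no dropout and no clustering by therapy group. The plan gives no rho, so a range is shown.

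**1. Reproducing N=64.** The normal approximation is n per arm = 2(1.960+1.282)² × 0.6²/0.5² = 30.3, so 31. The noncentral t gives 89.8% at 31 per arm and 90.7% at 32. N=64 is therefore the two-sample t-test figure. Other readings do not fit: a one-sided test needs 25 per arm, and a standardised effect of 0.5 needs 85.

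**2. Precision at one visit, score SD σ.**
- Change from baseline: variance 2(1−rho)σ².
- Baseline-adjusted: variance (1−rho²)σ².
- Ratio adjusted/change: (1−rho²)/[2(1−rho)] = (1+rho)/2.

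At rho 0.3 the ratio is 0.65, so the change analysis has 1/0.65 = 1.54 times the variance. At rho 0.5 it is 0.75, and the factor is 1.33. These ratios depend on neither N nor the meaning of 0.6.

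**3. Power with 64 analysed, 0.6 as the SD of a score, difference 0.5 at the visit tested.** Noncentral t; the adjusted test gives up one degree of freedom.

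| rho | SD of change | Power, change | Adjusted SD | Power, adjusted |
|---|---|---|---|---|
| 0.3 | 0.710 | 79% | 0.572 | 93% |
| 0.4 | 0.657 | 85% | 0.550 | 95% |
| 0.5 | 0.600 | 90.7% | 0.520 | 97% |

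The three-visit arm-by-time test (2 and 124 df) with the difference sustained at both follow-ups has 82.8%, 88.5% and 93.6% at the same correlations. If the difference halves by 6 months, it has 70.3%, 77.3% and 84.7%.

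**4. Power with 64 analysed, 0.6 as the SD of a change.** The single change contrast has 90.7% whatever rho is. The adjusted SD is 0.6√((1+rho)/2): 0.520 at rho 0.5 (96.6% power) and 0.553 at rho 0.7 (94.5%).

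**5. Power with about 120 analysed (8 × 15), 0.6 as the SD of a score.** The change contrast has 89% at rho 0 and 97% at rho 0.3.

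**6. Limit of the gain.** If the difference at 6 months is only 0.25, the adjusted comparison there, with 32 per arm and 0.6 as the SD of a score, has about 41%, 43% and 47% power at rho 0.3, 0.4 and 0.5.

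**The case against.** The strongest reply is that nothing here is shown to be short of power. The SD is undefined, and the trial is a pre-post design whose variability was studied in 30 randomised patients, so 0.6 may well be the SD of a change. In that case a single change contrast has the stated power with no condition on rho. The figure of 64 is also a minimum, and the group plan allows about 120. Finally, an arm-by-time test is unbiased in a randomised trial.

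All of this stands, and it rules out three stronger readings:

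- **That 90% is reached only if rho is about 0.45 to 0.6 or more.** That range needs 0.6 to be the SD of a score and exactly 64 patients analysed; its upper end also needs an effect that is half-size at one follow-up. The plan fixes none of these. Under the same SD reading, a contrast of the average follow-up with baseline and a sustained effect needs only about 0.32.
- **That the sample size has no slack.** The planned groups hold nearly twice the minimum.
- **That the planned test is biased by regression to the mean.** Over-correction of a chance imbalance is a matter of precision in the trial at hand, not a bias over randomisations.

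It is also fair to say that baseline as a level of time is inferred from the wording and the visit schedule, not written out. What the reply does not remove is the variance ratio (1+rho)/2, which is below 1 for any rho below 1 and applies at any sample size.

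**Conclusion.** The point holds as a free improvement. The planned comparison of changes is valid, but the baseline-adjusted comparison at one visit has only 65% of its variance at rho 0.3 and 75% at rho 0.5, from data already collected. This rests on similar SDs at baseline and follow-up.

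The effect on power depends on what the plan leaves open. It is substantial if 0.6 is the SD of a score and only 64 are analysed (79% against 93% at rho 0.3), modest if 0.6 is the SD of a change, and small with about 120 analysed. The documents support the statement that the SD is undefined; they do not support the statement that the trial is underpowered.

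A reader might also infer that adjustment secures 90% power in general. It does so at N=64 only for a true difference of 0.5 at the visit tested, with complete data, and ignoring dropout and clustering by therapy group. All power figures here are for tests of a difference, whereas the principal hypothesis under OBJECTIVES AND HYPOTHESIS is that one programme is at least as effective as the other.

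**What to change.** Replace the repeated-measures ANOVA sentence in METHODS with, for example:

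> SCS at 8 weeks and at 6 months will be compared between arms in a linear model with the two post-baseline visits as outcomes, allowing for correlation within patient, and with arm, visit, arm-by-visit, baseline SCS and baseline-by-visit as terms. The adjusted arm difference with its 95% confidence interval will be reported at each visit.

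Use the same form for CPAQ, BPI, the visual analogue scale, PCS, SF-36 and HADS, each with its own baseline.

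In the sample-size sentence, state whether 0.6 is the SD of a score or of a change, for which visit, and the correlation assumed, if any. Do not add a claim that the model guarantees 90% power.

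The cost is wording in two places and one degree of freedom per visit for the baseline term; no new data or patients are needed. The model yields two visit-specific differences, so the plan must still say how they lead to the primary conclusion.
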